#### 18.12 Study-specific data

Data	Description	Data type
Medication Satisfaction Questionnaire	"How satisfied are you with your medication?"	Categorical: Range 1-7
WHOQOL-BREF	26-item questionnaire measuring quality of life in 4 domains: physical health;	Continuous: Each domain score standardized to scores 0 (worse) to 100 (best)

	psychological health; social; environment	
Hospitalization 	Any Royal Victoria Regional Health Centre emergency room visits, admissions to hospital or mental health or detoxification centre since previous clinic visit (Yes: No)	Categorical
Reason for visit/admission	Opioid-related (Yes: No)	Categorical
Serious adverse events 	Hospitalization (for any reason)	Categorical
Reason	Opioid-related (Yes: No)	Categorical

 Only hospitalization events associated with the Royal Victoria Regional Health Centre are accessible to the RAAM clinic healthcare providers as they clinics share the same electronic health record system as previously described. All other hospitalizations would have to be self-reported by the participants and consent for access to the health records would then need to be secured by the RAAM clinic healthcare providers.

### 18.13 Healthcare utilization

This data (see Section 12.12) is available from the Registered Persons Database, Ontario Mental Health Reporting System, Discharge Abstract Database, and National Ambulatory Care Reporting System through the Institute for Clinical Evaluative Sciences using a data linkage with each patient's unique Ontario Health Insurance Plan number.

As a prescribed entity under the Personal Health Information Protection Act, the Institute for Clinical Evaluative Sciences is authorized to collect personal health information from health organizations without consent for the purposes of evaluation and monitoring of Ontario's health system. The Institute for Clinical Evaluative Sciences is prohibited, under its agreements with data providers, from contacting individuals whose information has been entrusted to the Institute for Clinical Evaluative Sciences. This contractual obligation restricts any opportunity to seek individuals' consent for use of their information for research.

The Institute for Clinical Evaluative Sciences will make available a research-ready, linked and risk-reduced coded dataset to the study investigators. Although highly de-sensitized, the research data is presented at an individual level. Study investigators will access the Research Data remotely on a secure, encrypted VMware virtual desktop called the Institute for Clinical Evaluative Sciences Data & Analytic Virtual Environment (IDAVE). Study investigators will perform analyses on IDAVE using statistical software. Research Data may not be copied or transferred from IDAVE. Only results derived from the Research Data that have been vetted for re-identification risk and approved by Institute for Clinical Evaluative Sciences may be released from IDAVE.

## 18.2 Retention

### 18.21 Strategies

Once a patient is enrolled or randomized, the RAAM clinics will make every reasonable effort to follow the patient for the entire study period. The RAAM clinics and their healthcare providers will utilize recommended clinical strategies as part of their usual standard of care to minimize loss-to-follow-up for any patient with OUD on opioid substitution therapy.

In addition to these strategies, the RAAM clinic healthcare providers and study personnel will:

- 1) Direct contact by phone for each participant will take place 2 days in advance of a scheduled clinic visit as a reminder of the date and time of the scheduled visit, and to determine if there are any barriers to attendance. Incentives such as taxi chits will be provided to participants who have transportation barriers to attendance.
- 2) For those participants who require additional bloodwork or electrocardiograms, home lab services free-of-charge will be provided through LifeLabs™.
- 3) The study-specific questionnaires will be completed using interviews with study personnel as opposed to simply asking participants to complete the questionnaires on their own to maximize completion rates.
- 4) The study-specific questionnaire schedules will be flexible, with study personnel able to interview participants  $\pm$  2 weeks around the scheduled date.

### 18.22 Withdrawal

Participants may choose to withdraw from the study for any reason at any time. As part of the usual standard of care, the RAAM clinic healthcare providers may also withdraw participants from the study for clinical reasons such as failure to comply with opiate substitution treatment, failure to comply with urine drug testing or self-reports of drug use, failure to attend scheduled clinic visits, failure to comply with birth control or becoming pregnant after enrolment, or for any other reason that may jeopardize the safety of the participants or others. For those participants who choose to withdraw or are withdrawn by their healthcare providers, ongoing follow-up for the study period will continue for all outcomes measured using routinely collected data (such as healthcare utilization). For outcome measures that require study-specific data, such as the WHOQOL-BREF questionnaire, consent will be sought to permit ongoing assessment for the study period. Deviations from the study protocol (which do not result in withdrawal by the healthcare providers) or loss-to-follow-up for any reason will not be considered reasons for withdrawal from the study.

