## 11.4 Modifications

For eligible patients randomly allocated to Sublocade®, missed doses can be administered up to 42 days after the last dose. For those with longer intervals between Sublocade® doses, it will be up to the discretion of the RAAM clinic healthcare providers whether repeated induction and stabilization with Suboxone® is required, and if Sublocade® treatment should be re-

initiated. At the discretion of the RAAM clinic healthcare providers, some participants may receive breakthrough doses of Suboxone® and/or an increased maintenance dose of Sublocade® of 300 mg per month instead of 100 mg per month as clinically indicated to prevent opioid cravings (VAS  $\geq$  21) or withdrawal (COWS  $\geq$  5) symptoms. In some cases, Sublocade® doses may need to be reduced or discontinued due to adverse effects.

For eligible patients randomly allocated to Suboxone®, at the discretion of the RAAM clinic healthcare providers, some participants may receive breakthrough doses of Suboxone® and/or increased maintenance doses of Suboxone® as clinically indicated to prevent opioid cravings (VAS  $\geq$  21) or withdrawal (COWS  $\geq$  5) symptoms. Daily dose of Suboxone® should not exceed 24 mg buprenorphine. In some cases, Suboxone® doses may need to be reduced or discontinued due to adverse effects.

For eligible patients with abnormal vital signs (a change from baseline measurements and any of the following: systolic blood pressure  $\leq$  90 mm Hg OR mean arterial blood pressure  $\leq$  55 mm Hg OR heart rate  $\geq$  130 beats per minute OR temperature  $\geq$  38.1°C OR  $\leq$  36°C OR respiratory rate  $\leq$  8 breaths per minute OR  $\geq$  30 breaths per minute or mental status (Glasgow coma scale  $\leq$ 14), RAAM healthcare personnel will investigate the causes for these abnormalities prior to consideration of buprenorphine dosing, and make all necessary arrangements for medical management of the patient.

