For eligible patients who have either a positive urine drug screen, illicit drug use by self-report, or refuse to submit to these screens, individualized patient counselling with an addictions counsellor will attempt to understand the underlying reasons for relapse or refusal to screen as per usual standard of care. RAAM healthcare personnel will take into consideration opioid positivity (either positive urine drug screen or self-report) or refusal to screen prior to the administration of study medications.

For eligible patients with a positive pregnancy test after a negative pre-enrollment test, RAAM healthcare personnel will counsel the patient about the potential negative effects (teratogenicity, neonatal opioid withdrawal syndrome) of ongoing study medication treatment, and the options for alternative management of OUD as per usual standard of care.

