### 12.11a Urine drug testing

The RAAM clinics perform on-site presumptive urine drug testing using Health Canada-approved, lateral flow immunoassay-based point-of-care tests (Rapid Response™ Multi Drug Test Panel, BNTX Inc., Product code: D-1P-07). This qualitative urine assay uses established cut-off values for addictive substances or their metabolites to identify their presence (positive) or absence (negative). The urine assay can detect the following addictive substances/metabolites: benzodiazepines, buprenorphine, cocaine, ethyl glucuronide, fentanyl, morphine, oxycodone, EDDP, hydromorphone, and methamphetamine. In addition, the assay also measures urine pH and urine creatinine to screen for specimen integrity. All results are available in 5 minutes. All RAAM clinic healthcare providers must receive training and certification before use of this assay, and biennial re-certification is required. Internal and procedural controls are included in the assay to indicate proper volume of specimen added and that wicking has occurred. In addition, the Royal Victoria Regional Health Centre Laboratory Services is responsible for quality control checks with each new lot number prior to release to the RAAM clinics for use. Definitive urine drug testing will not be used to validate the results of any urine drug test, but at the discretion of the RAAM clinic healthcare providers, may be used to investigate discrepancies between presumptive urine drug test results and self-reports, or detect unexpected addictive substances not available through presumptive testing. While urine sample collection is not directly observed by RAAM clinic healthcare providers, all urine samples must be collected during the clinic visit. To reduce the risk of urine tampering, each urine sample is inspected for temperature, colour, smell and appearance in addition to measuring urine pH and urine creatinine. Any urine sample that is considered substituted or invalid is discarded, and the patient will be imputed to have a positive urine drug test for that scheduled clinic visit. Urine drug screens and self-reports will only occur on day of the scheduled clinic visit, and there will be no opportunity to provide a urine sample either before or after the scheduled clinic visit.

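### Unmasked providers may withdraw participants from the study for non-compliance that overlaps the opioid endpoint, and nothing secures or explicitly scores the tests that would fall after withdrawal

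*Combined protocol and SAP*

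**What the plan says.** Section 18.22 allows withdrawal by the participant and also by the clinic: "the RAAM clinic healthcare providers may also withdraw participants from the study for clinical reasons such as failure to comply with opiate substitution treatment". The list goes on to "failure to comply with urine drug testing or self-reports of drug use, failure to attend scheduled clinic visits", and then to contraception, pregnancy and safety. No threshold or independent review is given. Section 17 states that providers are not masked.

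For withdrawn participants the same section says that "ongoing follow-up for the study period will continue for all outcomes measured using routinely collected data (such as healthcare utilization"). Section 18.11b lists urine toxicology and Timeline Followback, the two components of the opioid endpoint, among routinely collected data, under a table for the treatment period. Section 12.11a adds: "Urine drug screens and self-reports will only occur on day of the scheduled clinic visit".

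Section 12.11 sets the denominator as all weeks alive, at most 48. It scores a missed scheduled test, and the untested week before it, as not relapse-free. Section 20.11a restates only the rule for weeks with no scheduled test. Section 20.1 is intention-to-treat.

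Other text pulls towards keeping people in. Section 18.22 ends by saying that "loss-to-follow-up for any reason will not be considered reasons for withdrawal from the study". Under Section 18.21 the clinics "will make every reasonable effort to follow the patient for the entire study period". Under Section 11.4, after a positive or refused screen, "individualized patient counselling with an addictions counsellor will attempt to understand the underlying reasons for relapse or refusal to screen".

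**The concern.** A decision about treatment is allowed to become an exit from the study. The grounds for it (not taking treatment, not giving a sample or report, not attending) overlap the behaviour that the first primary endpoint scores as failure, and the person deciding knows the arm.

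Linked hospital records keep arriving without the participant. Urine tests and self-reports do not: they need a booked visit that is kept. If withdrawal ends the bookings, the intention-to-treat analysis has no opioid data from that date for people selected partly on how they were doing. If withdrawal is also more frequent in one arm, the treatment comparison moves. Tests that were not taken cannot be recovered afterwards.

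**Working it through.** **1. How the plan scores a missed test.** Figure 1 has 24 scheduled tests: 15 negative, 5 positive, 4 missing. Relapse-free weeks = 2 × 15 = 30, and 30/48 = 0.625, as the plan states. Missed scheduled tests therefore stay in the denominator and score as failures.

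**2. Withdrawal grounds against the endpoint.**

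| Ground in 18.22 | Effect on the endpoint |
|---|---|
| Not complying with testing or self-report | Missed scheduled test: two weeks not relapse-free |
| Not attending | Same |
| Not complying with treatment | Indirect |
| Positive test | Scored as failure, but not a listed ground |

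**3. After withdrawal.** Take a participant withdrawn at week 12 after six negative tests. If the remaining tests count as scheduled and missed, Section 12.11 gives 12/48 = 0.25, whatever happens in the other 36 weeks. If they are no longer scheduled, the missed-test rule does not literally apply, the off-week rule has no later result to copy, and Section 20.11a gives no code for the week.

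**4. Size under Section 12.11 scoring, simple form.** Assume no true difference. Let w be the proportion withdrawn, T the week of withdrawal, and r the relapse-free proportion that withdrawn participants would have had. Each withdrawn participant loses r × (48 − T)/48, so

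shift (Sublocade minus Suboxone) = (w_Suboxone − w_Sublocade) × r × (48 − T)/48.

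The documents give none of w, T or r. With T = 12 or 24 and r = 0.10 to 0.30:

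| Withdrawn, Suboxone vs Sublocade | Smallest (T = 24, r = 0.10) | Largest (T = 12, r = 0.30) |
|---|---|---|
| 20% vs 20% | 0 | 0 |
| 20% vs 10% | 0.10 × 0.10 × 0.50 = 0.005 | 0.10 × 0.30 × 0.75 = 0.022 |
| 30% vs 10% | 0.20 × 0.10 × 0.50 = 0.010 | 0.20 × 0.30 × 0.75 = 0.045 |
| 50% vs 20% | 0.30 × 0.10 × 0.50 = 0.015 | 0.30 × 0.30 × 0.75 = 0.068 |

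Reversing the imbalance reverses the sign.

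**5. Size when withdrawal follows poor results.** Assume that each participant has a chance p of a negative result at each of the 24 tests, with p distributed Beta(0.4, 0.6) in both arms (mean 0.40), and a withdrawal chance h after each non-negative test. The chance of staying past one test is s = 1 − h(1 − p). Then

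- proportion withdrawn = 1 − E[s^24]
- mean score = E[p × (1 + s + … + s^23)]/24

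| h | Withdrawn | Mean score |
|---|---|---|
| 0.02 | 24% | 0.3744 |
| 0.04 | 41% | 0.3524 |
| 0.08 | 61% | 0.3165 |

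With h = 0.02 on Sublocade, the false difference is 0.3744 − 0.3524 = +0.022 if h = 0.04 on Suboxone, and 0.3744 − 0.3165 = +0.058 if h = 0.08. Against the 0.15 target these are 0.022/0.15 = 15% and 0.058/0.15 = 39%. Equal h gives zero.

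The result does not need positive tests to trigger withdrawal. If 40% of non-negative tests are missed tests (an assumption; Figure 1 has 4 of 9, or 44%) and only a missed test can trigger it, chances of 5%, 10% and 20% per missed test give h = 0.4 × 0.05 = 0.02, 0.4 × 0.10 = 0.04 and 0.4 × 0.20 = 0.08, and the same table. These are shifts in simple mean proportions, not in the fitted model.

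**The case against.** The plan has a fair defence. Section 18.22 continues routinely collected outcomes, Section 18.11b counts the opioid data among them, Sections 12.11 and 13 schedule tests every two weeks to week 48, no text cancels visits, and Section 20.11a points back to Section 12.11. Read together, the denominator does not stop at withdrawal. That stands. What it does not supply is a statement that a withdrawn participant is still booked, least of all one withdrawn for not attending.

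Four stronger readings are tempting, and the documents do not support them.

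- **Follow-up for the opioid endpoint ends at withdrawal.** It can lapse in practice; the text does not end it.
- **The grounds are the outcome itself.** They overlap it. A positive result is not a listed ground, and Section 11.4 answers it with counselling.
- **Withdrawal will be unequal, and higher on Suboxone.** No arm-specific rate is given. In the Sublocade arm "missed doses can be administered up to 42 days after the last dose", but that is a late-dose rule and not a definition of compliance. Suboxone may become unsupervised after two weeks (Section 11.1), while a missed injection is visible in the clinic, so the imbalance could run either way.
- **Leaving the empty weeks out of the model would reverse the bias.** A crude pooled proportion would suggest so. A random-intercept logistic model of the kind planned in Section 20.11a, fitted to the step 5 set-up with withdrawal triggered by observed positive tests, brought the difference to within 0.1 point of zero. That fit had no clinic level and no week interaction. Withdrawal that depends on unobserved use was not examined.

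The last sentence of Section 18.22 can also be reconciled with the grounds, since it exempts deviations that did not lead to withdrawal by the provider. It supports retention, and deleting it would weaken the plan.

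**Conclusion.** The point holds as a gap in the rules, not as a demonstrated bias. Unmasked, discretionary withdrawal from the study is permitted on grounds that overlap the endpoint. Collection of opioid data afterwards depends on visits that no text keeps booked, and the analysis section does not carry over the missed-test rule.

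A shift of about +2 to +6 points towards Sublocade is an illustration. It assumes withdrawal of about 24% against 41% to 61%, a mean relapse-free proportion of 0.40, and Section 12.11 scoring. Milder imbalances in step 4 give 0.5 to 4.5 points. This should be fixed, with moderate confidence about its practical effect. It is a cheap improvement, worth making before enrolment.

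**What to change.** - Amend Section 18.22 to distinguish stopping or changing study drug from leaving the study.
- Remove non-compliance with treatment, testing, self-report or attendance as grounds for provider withdrawal from the study. Treatment and safety decisions stay with the provider; record their date and reason.
- State that the two-weekly urine test and Timeline Followback stay booked to week 48 for everyone who has not withdrawn consent, where safe, whatever treatment they are on.
- Write the Section 12.11 missed-test rule into Section 20.11a, including weeks after withdrawal. Report withdrawals and reasons by arm, and add a sensitivity analysis that handles those weeks differently.
- Keep the sentence on loss to follow-up, and reconcile it with the withdrawal grounds, the counselling text in Section 11.4 and the follow-up commitment in Section 18.21.

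The cost is a wording amendment, a case report form field for date and reason, and one extra analysis. Some scheduled tests and reminder calls will continue for participants who are off study drug.

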## 19 Data management

All routinely collected data will be entered electronically by the RAAM clinic healthcare providers at the RAAM clinics using the electronic health record system. Study personnel will extract the relevant routinely collected data from the electronic health record system and record the data into the electronic case report form stored in REDCap, a password-protected, Personal Health Information Protection Act (PHIPA)-compliant database stored on servers at the Royal Victoria Regional Health Centre that is used to support all the hospital's research activities and is supported and managed by the staff of the Royal Victoria Regional Health Centre Research Institute. Study personnel will record study-specific data directly into the REDCap electronic case report form (Medication Satisfaction Questionnaire and WHOQOL-BREF questionnaire) or extract study-specific data from the electronic health record system (Healthcare utilization) and record it in REDCap. The study personnel will access the questionnaires (Medication Satisfaction Questionnaire and WHOQOL-BREF questionnaire) in REDCap and complete them with the participants. This may be done either in-person at the RAAM clinics or remotely by telephone or videoconference.

When a patient is enrolled and randomized, a unique study number will be automatically generated in REDCap. This unique study number, along with the patient's name (first, middle, last), Ontario Health Insurance Plan number, date of birth, and unique electronic health record system number will be stored in a password-protected EXCEL computer file. This study EXCEL file will be stored in a dedicated, password-protected electronic shared drive located on the Royal Victoria Regional Health Centre Personal Health Information Protection Act (PHIPA)-compliant servers. This EXCEL file will permit linkage to the electronic case report form to enable study personnel to record repeated measurements over the study period for a participant. Real-time data quality rules will be implemented in REDCap that will display warning pop-up messages whenever the rules are violated during data entry. These quality rules will minimize missing values in required fields; prevent incorrect data type entry and out of range data entry; identify outliers for numerical fields; and prevent invalid data entry into multiple choice fields. The data quality rules will also be available to be executed at any time by a study monitor or study personnel. All electronic case report form entries and edits are associated with an electronic audit trail that identifies the user, date and time of entry, and entry type. The type of activity that study personnel may undertake in REDCap is regulated by privileges associated with their user identification and password. Incremental data back-ups of REDCap are routinely performed twice a day, with off-site storage of the backed-up files done on a monthly basis. Data status reports on missing data will be provided to the Data management committee on a biweekly schedule for review. All study data will be archived in REDCap for 25 years and subsequently permanently destroyed.

## 20 Statistical methods

### 20.1 Outcomes

The intervention arm (Sublocade®) will be compared against the active comparator (Suboxone®) for all primary and secondary analyses. All analyses will be done according to original patient allocation regardless of whether they received the randomized treatment or were compliant with the study protocol (Intention-to-treat). All analyses will be conducted using STATA/MP 17.0 for Mac.

## 20.11 Primary

### 20.11a Opioid positivity

We will use a 3-level hierarchical design to model the relapse-free weeks data where the observation for each week (Level 1) will be coded as binary; relapse-free week if urine drug screen and self-report is negative for non-prescribed opioid use, and otherwise relapse week if either is positive for non-prescribed opioid use. As described in Section 12.11, imputation of missing data will occur for those weeks in which a urine drug screen/self-report was not scheduled according to the results of the subsequent week's urine drug screen/self-report. Level 1 observations are clustered within individual participants (Level 2), which are nested within RAAM clinic sites (Level 3). We will analyse the outcome data using multi-level, mixed-effects logistic regression analysis with random effects estimated for the variance in the intercepts of both participant and clinic levels. The model will also include a random slope on the indicator for OUD severity (moderate versus severe) in the Level 2 random effects equation using an unstructured covariance structure between intercept and slope. We will also include clinic visit (week) and an interaction term between clinic visit and treatment. A sensitivity analysis will be conducted to compare this baseline model with an extended model that includes any baseline demographic or clinical variables that appear to be unbalanced at Level 1. The models will be compared using the likelihood-ratio comparison test for superiority. Post-regression analyses using *margins* command will be used to estimate difference in proportions of RFWs between treatment groups.

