## 12 Outcomes

### 12.1 Primary outcome measures

#### 12.11 Opioid positivity

Difference in proportions of relapse-free weeks (RFWs) at 12-months from the date of randomization, where ***relapse-free weeks are defined by the cumulative number of weeks alive during the study period in which there was a negative urine drug screen and negative self-report for non-prescribed opioids.*** The potential number of RFWs for each patient is the cumulative number of weeks that the patient is alive during the 12-month study period, with a maximum of 48 weeks. A week is defined as a consecutive 7-day period starting on the day of the week that randomization occurred. A patient is considered to have 'completed' a week as long as they are alive for  $\geq 1$  day of that week. For example, if a patient is randomized on a Tuesday, and subsequently dies on a Thursday of the 32nd week, the patient will have been considered to have been alive for 32 weeks. The denominator used in estimating the proportion of RFWs will be the total number of weeks that the patient was alive during the study period. Vital statistics for all participants (date and year of death) will be available through linkage with the Office of the Registrar General of Ontario database. The cumulative number of RFWs alive will be used as the numerator in estimating the proportion of RFWs. Scheduled urine drug testing and self-reports will occur every 2 weeks during the study period starting in week 2 from randomization. Imputation of missing data will occur for those weeks in which a urine drug screen/self-report was not scheduled according to the results of the subsequent week's urine drug screen/self-report. For example, if a urine drug screen/self-report was not scheduled for week 11, but a scheduled urine drug screen/self-report was done on week 12 and week 12 met the criteria for a RFW, then week 11 would be imputed as a RFW (Figure 1). Similarly, for weeks with scheduled urine drug screen/self-reports that are missed, that week and the preceding week in which there was no scheduled urine drug screen/self-report will not be counted as RFWs (for example, see Figure 1, week 17 and 18). In the hypothetical patient represented in Figure 1, 20 urine drug screens/self-reports were completed, with 5 positive and 15 negative urine drug screens/self-reports, resulting in 30 cumulative RFWs over the 48-week study period, or a proportion of RFWs of 0.625.

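### Copying each test result into the week before it leaves the overall treatment contrast intact but makes the standard error of the visit-by-treatment term too small by about the square root of 2

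*Combined protocol and SAP*

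**What the plan says.** All references are to the combined protocol and SAP.

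- **Outcome (Section 12.11).** The RFW proportion has the weeks alive as denominator, "with a maximum of 48 weeks". On the schedule: "Scheduled urine drug testing and self-reports will occur every 2 weeks during the study period starting in week 2 from randomization".
- **Unscheduled weeks (Section 12.11).** Each takes the result of the following week. In the worked example, if week 12 is relapse-free, "then week 11 would be imputed as a RFW". If the scheduled test is missed, "that week and the preceding week in which there was no scheduled urine drug screen/self-report will not be counted as RFWs". Either way the two weeks of a pair carry the same value.
- **Model (Section 20.11a).** In a mixed-effects logistic model "the observation for each week (Level 1) will be coded as binary", and the copying rule is repeated: "imputation of missing data will occur for those weeks in which a urine drug screen/self-report was not scheduled". The dependence modelled is "random effects estimated for the variance in the intercepts of both participant and clinic levels", plus a random slope on opioid use disorder (OUD) severity.
- **Time (Section 20.11a).** "We will also include clinic visit (week) and an interaction term between clinic visit and treatment". Whether week is linear or a factor is not stated.
- **Treatment effect (Section 20.11a).** The difference in RFW proportions comes from post-regression margins. Whether these average over weeks or are taken at chosen weeks is not stated.

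No robust variance, weighting or pair-level effect is described. The row count is not given; 48 follows from the weekly unit and the 48-week maximum.

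**The concern.** A mixed logistic model treats rows as independent given the random effects. The participant intercept, the clinic intercept and the severity slope are all constant within a patient, so none of them can absorb the fact that week 11 is a copy of week 12. The copy carries no information, yet the likelihood counts it as a second result.

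Terms estimated from change within a patient then look twice as well informed as they are. The planned visit-by-treatment interaction is such a term. A reader of the fitted primary model could conclude, on error bars that are too narrow, that the treatment difference grows or fades over the year. The participant variance reported from the same model would also be too large.

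**Working it through.** **1. Inputs.** 48 weeks and a test every 2 weeks from week 2 (Section 12.11) give 48/2 = 24 real results. There are 45 patients per arm, a comparator RFW proportion of 0.3 and a two-sided 5% level (Section 14.4). The random-intercept SD on the logit scale is not in the documents. It is an assumption, shown over a range.

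**2. The plan's own example.** Figure 1 has 24 scheduled tests: 15 negative, 5 positive, 4 missed. 2 × 15/48 = 0.625, as stated. The same patient on one row per test gives 15/24 = 0.625. The running count in Figure 1 moves only in steps of 2, which confirms the identical pairs.

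**3. Theory for the interaction (1 df, week linear).** Entering each result twice doubles the model's information on a within-patient slope, while the true spread of the estimate is unchanged. Model SE ≈ true SE/√2 = 0.707 × true SE. The real size of a nominal 5% test is 2 × [1 − Φ(1.96/√2)] = 2 × [1 − Φ(1.386)] = 16.6%.

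**4. Simulation under no effect.** 24 tests per patient, mean RFW proportion 0.3 in both arms, random-intercept logistic model fitted by quadrature, week linear, Wald tests at 1.96. Each dataset was fitted on 24 rows and again on 48 copied rows. Entries are false-positive rates.

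| Random-intercept SD (binary-scale ICC) | Datasets | Interaction, 24 rows | Interaction, 48 rows | Overall difference, 24 rows | Overall difference, 48 rows |
|---|---|---|---|---|---|
| 1 (0.16) | 1,500 | 3.9% | 16.1% | 5.9% | 6.2% |
| 2 (0.38) | 1,000 | 4.4% | 14.8% | 3.8% | 4.2% |
| 3 (0.52) | 1,000 | 6.3% | 19.9% | 5.2% | 5.1% |
| 6 (0.74), finer quadrature grid | 600 | 4.7% | 16.7% | 6.0% | 5.7% |
| 2 (0.38), common time trend | 1,000 | 4.1% | 15.8% | 6.4% | 6.4% |

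The interaction SE on 48 rows was 0.715 to 0.718 of its 24-row value, against 0.707 in theory. Separate runs at SD 1 to 2 gave 3.9% to 6.0% on 24 rows and 14.8% to 18.8% on 48.

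**5. Why the overall difference survives.** It compares patients with patients. The SE of the margins difference on 48 rows was 1.00 to 1.01 of its 24-row value. The copied rows make the model assign within-patient noise to the participant effect instead. The median estimated participant SD rose from 0.98 to 1.09 (SD 1) and from 5.91 to 6.84 (SD 6), ratios of 1.11 and 1.16. Over all scenarios the excess was about 10% to 16%, so the variance is overstated by about 21% (1.10² = 1.21) to 35% (1.16² = 1.35).

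**6. Margins at single weeks (week linear).** The 48-row SE was about 0.95 of the 24-row SE at the first and last visits and about 1.01 at mid-study. False positives at weeks 2 and 48 went from 5.4% and 4.6% to 8.5% and 7.9% at SD 1, and from 6.8% and 4.8% to 7.6% and 5.4% at SD 2.

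**7. Is one row per test enough?** Not if results are dependent beyond the random intercept. Missed tests are scored as failures, so dropout creates runs of failures. Section 14.3 mentions a loss to follow-up of 20% in an earlier study and assumes 50% as a worst case. Interaction size under no treatment effect, 300 datasets each:

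| Situation | 24 rows | 48 rows |
|---|---|---|
| 20% dropout | 10.3% | 30.7% |
| 50% dropout | 21.0% | 38.7% |
| Serial correlation 0.8 (assumed) | 12.7% | 31.3% |

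**The case against.** The strongest reply is that no planned inference rests on the inflated term. The hypothesis (Section 6), the primary objective (Section 7.1), the outcome (Section 12.11) and the sample size (Section 14.4) all concern the overall level of opioid positivity or the RFW proportion. No section plans a formal test of the interaction or a claim about change over time. This stands, and it limits the weight of the point.

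Three stronger readings might be inferred, and the material supports none of them:

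- **That the primary treatment test is inflated.** The overall margins difference kept its size and its SE (steps 4 and 5).
- **That week-specific margins are wrong by the square root of 2.** They are about 5% too precise at the first and last visits and not at all in the middle, and the plan does not commit to reporting them.
- **That one row per test by itself restores 5%.** It does so only when tests are independent given the random intercept (step 7).

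It can also be said that the row count and the coding of week are inferred. That is so. But a weekly Level 1 unit, with the copying rule restated in the analysis section, is most naturally read as weekly rows. If 24 rows are intended, the SAP needs to say so.

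**Conclusion.** The point holds for the visit-by-treatment term and the participant variance, and not for the primary contrast. The model-based SE of the interaction is too small by about √2. Its false-positive rate is about 15% to 20% instead of 5% (theory 16.6%), or roughly one null trial in six.

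That figure assumes weekly rows, a linear week and tests independent given the random intercept. Dropout runs or serial correlation make it worse. If visit were a 24-level factor, the 23-df interaction test would have an analytic size of about 78%. The simulations omitted the clinic intercept and the severity slope; both are constant within a patient and do not model the copied pairs.

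The change is worth making before analysis because the interaction is a planned part of the primary model and its error bars would be wrong.

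**What to change.** In Section 20.11a:

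1. Fit the model to one row per scheduled test, up to 24 per patient, with a missed test scored as not relapse-free as now. This removes the copied rows and the overstated participant variance.
2. Use patient-clustered robust standard errors, to cover runs of missed tests and serial correlation. Their performance here was not simulated. The SAP should say how they are obtained alongside the clinic intercept: a three-level likelihood separates by clinic, so a robust variance taken at its top level would rest on only four clusters. Fixed clinic indicators are one way round this.
3. State whether week is linear or a factor, and whether margins average over weeks.
4. Keep the 48-week RFW count for description, where each test still stands for two weeks.

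The cost is SAP wording and a differently shaped analysis file; no new data, visits or patients are needed. There is one small downside. Section 12.11 counts any week with at least one day alive, so a patient who dies in an odd week has a last week in the denominator with no test attached. The SAP should state how that week is handled.
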